#### 6.0 Study Procedures

#### Study Design

The proposed study is a prospective randomized controlled trial among children admitted to the ICU setting at Vanderbilt Children's Hospital (VCH). Enrolled subjects will receive one of two management strategies: 1) Standard of care with antimicrobial stewardship review (control), or 2) PCT testing and treatment with antimicrobial stewardship review (intervention). All subjects in both arms will have baseline audit of antimicrobial orders with feedback to providers by the antimicrobial stewardship team. For subjects in the intervention arm, the stewardship team will additionally recommend PCT testing and treatment per algorithm (Fig 1). PCT will be used in conjunction with clinical status and exam, and results of radiographic and laboratory studies, to make medical decisions about antibiotic therapy. The PCT will never be used as the sole basis for making decisions to modify or stop antibiotic therapy. The antibiotic stewardship clinicians will review all enrolled subjects (in control and intervention arms) and provide recommendations regarding antimicrobial therapy.

The ultimate decision to obtain PCT testing and/or adhere to the PCT algorithm or stewardship recommendations will be at the discretion of the ICU attending physician. Preliminary discussions with ICU faculty have revealed that they are highly supportive of the proposed study, and would be willing to adhere to the study protocol.

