- 2. Median time from randomization to first appropriate antibiotic escalation or de-escalation based on patient's clinical status and available supporting laboratory evidence, or lack thereof, of specific type of infection within 14-days post randomization.

Clinical Outcome Measures

- 1. In-hospital mortality within 30 days of randomization.
- 2. Length of stay in the hospital after randomization, up to 30 days, for those patients alive at 30 days. Length of stay will be date of discharge minus date of randomization.
- 3. Days in the ICU during hospitalization after randomization, up to 30 days, for those patients alive at 30 days.
- 4. Days spent using invasive ventilation methods (not including supplementary oxygen via nasal cannula or Vapotherm support) within 14-days post randomization.
- 5. Number of antibiotic-associated complications per patient within 14-days post randomization.
- 6. Acquisition of new hospital-acquired infections (HAIs) and/or multidrug resistant organisms (MDROs) within 30 days during index hospitalization identified on routine clinical or surveillance samples
- 7. Hospital re-admission within 30 days (yes/no)

Post Hoc Exploratory Analyses

- 1. Median DOT per patient of intravenous antibiotic therapy (in days) within 14-days post randomization
- 2. Antibiotic use > 72 hours (categorical) for any antibiotic, broad-spectrum antibiotics or IV antibiotics.
- 3. Count (%) of patients on 2 or more antibiotics at 24, 48, 72 and 96 hours after enrollment.
- 4. Total number of antibiotic stewardship recommendations made in each arm within 48-hours post randomization.

ProPICU: Statistical Analysis Plan

June 4, 2019

- 5. Rate of clinical provider compliance with adherence to suggested antibiotic escalation or de-escalation made by the antimicrobial stewardship team.
- 6. The primary endpoint will be analyzed comparing patients who:
 - Have antibiotics initiated due to concern for sepsis
 - Receive a clinical diagnosis of pneumonia
 - Have initial procalcitonin levels <0.5 ng/mL versus >0.5 ng/mL
 - Have no comorbidities versus those with comorbidities
 - Are in the pediatric intensive care unit at randomization
- 7. Number of antibiotic stewardship recommendations made in each arm within 48-hours post randomization will be analyzed (chi2 value will be compared between groups):
 - Male vs. female patients
 - Patients who receive a clinical diagnosis of pneumonia
 - Patients who have antibiotics initiated due to concern for sepsis

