Table summaries will present the following study population characteristics by randomized arm. All variables, as noted below, will be analyzed on the continuous scale or as categories or both as appropriate.

For continuous variables, summary statistics will include # of participants and median (Q1-Q3).

For categorical variables, summary statistics will include number (%) for each category. In calculation of percentages, participants with missing data will not be included in the denominator.

We will calculate the median days of antibiotic therapy per patient within the first 14-days post randomization in both treatment arms, together with the interquartile range. The primary test will be a Wilcoxon rank-sum test without the assumption of normality.

We will compare other continuous outcomes using a Wilcoxon rank-sum test, and categorical outcomes using a Pearson's chi-squared test.

We will perform a post-hoc analysis using a multivariable ordinal logistic regression model to assess the association between randomization group and the overall antibiotic duration of therapy per patient, adjusting for sex, recent surgical procedure, antibiotic indication of possible sepsis, and fever, vasopressor support and need for mechanical ventilation at enrollment.

We will perform a Cox proportional odds model adjusting for location of enrollment and study day to evaluate the hazard ratio for time to cessation of antibiotics within 4-days and within 10-days.

Final Analysis Considerations

The primary analysis will be a modified intention to treat (ITT) analysis. Participants who died prior to randomization, underwent bone marrow transplant or solid organ transplant prior to or after randomization, who are diagnosed with cystic fibrosis, or who ultimately are diagnosed with endocarditis, osteomyelitis, meningitis, mediastinitis or other invasive infection for which long duration of antibiotics is needed will be considered unevaluable. These are all issues that would otherwise qualify as exclusion criteria at the time of enrollment.

1. Study Population

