Table: Days of antibiotic therapy per patient within 14 days, restricted to patients with a final diagnosis of pneumonia.

Table: Days of antibiotic therapy per patient within 14 days, restricted to patients with sepsis as their indication for antibiotics.

Table: Days of antibiotic therapy per patient within 14 days, restricted to patients with an initial procalcitonin level < 0.5 ng/mL.

Table: Days of antibiotic therapy per patient within 14 days, restricted to patients with an initial procalcitonin level > 0.5 ng/mL.

5. Antimicrobial Stewardship

Table: Number (%) of patients with a stewardship recommendation made within 48-hours of enrollment

Table: Number (%) of stewardship recommendations accepted in each arm

Table: Number (%) of recommendations to de-escalate therapy

Table: Number (%) of recommendations to escalate therapy

Table: Number (%) of recommendations to optimize dose

Table: Number (%) of recommendations to consult the infectious diseases service

Table: Number (%) of recommendations to de-label a beta-lactam allergy

ProPICU: Statistical Analysis Plan

June 4, 2019

Table: Number (%) of recommendations that were not accepted due to provider discretion

Table: Number (%) of recommendations that were not accepted due a patient medication allergy

Table: Number (%) of recommendations that were not accepted due provider waiting for 48-hour culture results

Table: Number (%) of recommendations that were not accepted due to unknown reasons

Table: Number (%) of any antibiotic change that was initiated by pediatric intensive care provider, pediatric infectious diseases provider or stewardship provider

Table: Number (%) of antibiotic escalation that was initiated by pediatric intensive care provider, pediatric infectious diseases provider or stewardship provider

Table: Number (%) of antibiotic de-escalation that was initiated by pediatric intensive care provider, pediatric infectious diseases provider or stewardship provider

6. Clinical Outcomes

Table: Number (%) of death within 30 days of randomizationMedian time from randomization to death among patients who died

Table: Median length of stay within 30 days after randomization

Table: Median length of ICU stay within 30 days after randomization

Table: Number (%) with antibiotic complication

Table: Number (%) with infection with multi-drug resistant organism

Table: Number (%) with hospital re-admission within 30 days

7. Sensitivity analysis

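### Most stewardship tables count recommendations, not children: an unadjusted chi-squared test may give p-values that are too small, and the percentage accepted has a denominator that depends on the arm

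*SAP*

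**What the plan says.** The first table in SAP section 5 counts children: "Table: Number (%) of patients with a stewardship recommendation made within 48-hours of enrollment". The tables after it change the unit. Acceptance is given as "Table: Number (%) of stewardship recommendations accepted in each arm". The types of recommendation and the reasons for non-acceptance are also numbers and percentages of recommendations, and the last three tables count antibiotic changes by who initiated them.

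Two places bear on testing. The Analysis Plan (SAP part F, Statistical Considerations) compares "categorical outcomes using a Pearson's chi-squared test" and sends continuous outcomes to a Wilcoxon rank-sum test. Item 7 of the exploratory list reads "Number of antibiotic stewardship recommendations made in each arm within 48-hours post randomization will be analyzed (chi2 value will be compared between groups", and then names subgroups. Items 4 and 5 of that list are "Total number of antibiotic stewardship recommendations made in each arm within 48-hours post randomization" and "Rate of clinical provider compliance with adherence to suggested antibiotic escalation or de-escalation made by the antimicrobial stewardship team", with no test, and item 5 has no unit or denominator. The list is headed "Post Hoc Exploratory Analyses".

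The SAP does not limit a child to one recommendation and makes no allowance for several from the same child. On how the arms differ, the protocol says (section 6.0, Study Design): "For subjects in the intervention arm, the stewardship team will additionally recommend PCT testing and treatment per algorithm (Fig 1". The implementation subsection adds daily record review and in-person rounds to press for adherence in the intervention group.

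**The concern.** There are two separate problems.

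**Unit.** Pearson's chi-squared test treats every counted item as independent. Several recommendations for one child concern the same illness and largely the same clinicians, so their acceptance is likely to be correlated. Repeats are plausible: stewardship review is daily, standard care may involve more than one antibiotic, and PCT is measured several times in the intervention arm. Pooling such items understates the variance.

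**Denominator.** Whether a recommendation exists is decided after assignment, and the intervention arm generates additional ones. The percentage accepted is therefore taken over a different number and mix of recommendations in each arm. This needs no assumption about correlation and would remain with one recommendation per child.

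What is at stake is interpretation. The protocol's rationale is that clinicians in earlier trials often did not follow PCT guidance (up to 50%), and adherence to the algorithm is one of its secondary outcomes. Acceptance rates are likely to be used to explain the primary result, whichever way it falls.

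**Working it through.** **Inputs.** The documents give no number of recommendations per child, no acceptance rate and no intra-child correlation (ICC), so there is no planned figure to reproduce. The nominal level of 0.05, two-sided, is the one in protocol section 10.0. The counts, the ICC and the 70% acceptance used below are assumptions.

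**Step 1: inflation from pooling.** If each child has a Poisson number of recommendations with mean λ (zero allowed), the variance of a pooled proportion is multiplied by about D = 1 + λ × ICC. The actual level of a nominal 5% test is 2 × [1 − Φ(1.96/√D)].

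| λ | ICC 0 | ICC 0.1 | ICC 0.3 | ICC 0.5 |
|---|---|---|---|---|
| 1 | 5.0% (D = 1) | 6.2% (D = 1.10) | 8.6% (D = 1.30) | 11.0% (D = 1.50) |
| 1.5 | 5.0% (D = 1) | 6.8% (D = 1.15) | 10.4% (D = 1.45) | 13.8% (D = 1.75) |
| 2 | 5.0% (D = 1) | 7.4% (D = 1.20) | 12.1% (D = 1.60) | 16.6% (D = 2.00) |

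Simulation agrees. With 140 children per arm (the SAP's 280, assumed to split equally), 70% acceptance, no true difference and 20,000 trials per setting, ICC 0.3 and 0.5 gave 8.3% and 11.1% at λ = 1, 10.4% and 14.1% at λ = 1.5, and 12.1% and 16.4% at λ = 2.

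A Poisson mean of 1 does not mean one recommendation each. It implies that 1 − 2e⁻¹ = 26% of children have two or more, and that children with any average 1/(1 − e⁻¹) = 1.6. If every child with a recommendation has exactly one, D = 1 and the level is 5% at any ICC; a separate simulation of that case gave 4.9% to 5.4%.

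**Step 2: the arm-dependent denominator.** Suppose both arms have the same 70 shared recommendations, accepted at 70% (49 of 70), and the algorithm adds 70 more in the intervention arm.

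- Extras accepted at 50%: (49 + 35)/140 = 60%, against 70% in control.
- Extras accepted at 90%: (49 + 63)/140 = 80%, against 70% in control.

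No shared recommendation is handled differently, yet the arms differ by 10 percentage points, in either direction.

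**Step 3: is the child an independent unit?** Not fully. The SAP's Design entry describes a pre-assigned cluster multiple crossover trial, and its baseline table records one of 20 attending physicians. Correlation by unit, period and attending comes on top of Step 1 and is not in those figures.

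**The case against.** The strongest reply is that the SAP does not say these tables will be tested. A number and percentage is also how it summarises any categorical variable, so the acceptance, reason and initiator tables may be purely descriptive. This stands in part: the chi-squared test is inferred for the acceptance table from the general rule. It is explicit only in item 7, for numbers of recommendations within 48 hours. Even there, the matching 48-hour table counts children, so the test might be meant at child level; but item 7 as worded names the number of recommendations.

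A reader might infer that all the stewardship comparisons use the wrong unit and that their p-values are certainly too small. The documents do not support this. The first table is at child level, and inflation needs both repeated recommendations and positive correlation, neither of which is given. Some types, such as removing an allergy label or consulting infectious diseases, are unlikely to recur in a child.

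A reader might also take the changing denominator as a cause of small p-values. It is a possible bias of unknown direction, which is a different matter. Nor is a change in the number and mix of recommendations itself a flaw: the SAP lists the algorithm's effect on recommendations as an exploratory objective, and section 5 reports the mix by type. Only the reading of the acceptance percentage as an effect of assignment is affected.

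Finally, the analyses are labelled post hoc exploratory. That stands and sets the severity.

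**Conclusion.** The point holds in a limited form and is minor. All section 5 tables but the first count recommendations or antibiotic changes, and the only categorical test on offer takes no account of repeats within a child. If that test is applied and children have several correlated recommendations, the true level of a nominal 5% test is about 6-7% at ICC 0.1 and about 8-17% at ICC 0.3-0.5, for Poisson means of 1 to 2. It stays at about 5% if there is one recommendation per child or no correlation. All of these rest on assumed counts and correlations.

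The denominator problem does not rest on those values. It follows from the protocol's own description of the intervention arm; only its size and direction are unknown. The primary result is unaffected by either problem.

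**What to change.** 1. Replace the chi-squared test on pooled counts with a comparison, over all assigned children (zeros included), of recommendations per child and of accepted recommendations per child. Use a rank test, which the SAP already uses for continuous outcomes, or a negative binomial model.
2. Define the unit, denominator and time window for the compliance rate and the acceptance table. The 48-hour window is stated for the counts but not for these.
3. Present per-recommendation acceptance as descriptive, with cluster-robust intervals by child, and show PCT-triggered recommendations separately from the others. The proportion of children with at least one accepted recommendation is no substitute for an acceptance rate, because it rises when more recommendations are made.
4. Account for unit and period, as the cluster-crossover design requires. The SAP's Cox model already adjusts for place of enrollment and study day, so the variables should be available.

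The cost is SAP wording, plus a flag for PCT-triggered recommendations if none is recorded. Per-recommendation intervals become somewhat wider: standard errors grow by √D, which is √2.0 = 1.41, or about 40%, at mean 2 and ICC 0.5, and less at lower values.
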